#### **4.7 Product Accountability Procedures**

The study investigators will be responsible for patient safety during the study. Capsulin use will be monitored using the cap tracker count (Aardex history), the study logbook, the patient's pump data, and a manual count of the remaining capsules.

#### **4.8 Trial Duration/Schedule**

Expected duration of the study is 12 months. Each participant's time in the study is 12 weeks. The visits, assessments and visit duration for every participant is listed in the table below.

Visit Sequence	Visit Duration	Assessments	Comment
VISIT 1 (Week0)  STUDY START	8.5h	Informed Consent confirmed.	
		Height, weight, BP, Date of Birth, Date of Diagnosis, Date of pump start, Date of start of closed loop  Pump download for pump settings and CGM data	Ensure participants are well and that the prior two weeks representative of routine diabetes management
		Glycaemic measures: HbA1c, total insulin dose, insulin sensitivity factors, insulin-carbohydrate ratios and CGM metrics	
		Metabolic measures (2mls blood): lipid profile, liver function tests	Fasting bloods
		Meal Challenge (following an overnight fast) with standard SC pre-meal bolus via pump.  Measure gut hormone responses over 5h - plasma GLP-1 (glucagon like peptide), GIP (glucose dependent insulinotropic polypeptide), plasma glucagon and free insulin.  A total of 106 mls will be drawn for 15minutely blood BGL testing and gut hormones during the meal challenge.	SC bolus to be administered for standard meal. Meal is to be eaten within 20 minutes under supervision. No other oral intake (excluding water) for the next five hours.
		Dexcom G6 set-up and training for those on 670G. Provided with sufficient sensors for 2 weeks .	As Medtronic 670G users do not have the follow-function (available with 770G), participants using 670G will be offered an additional continuous glucose monitor (Dexcom G6) to obtain glucose data during the first three weeks of the study period. The device has a share function which will permit the research staff to review the glucose levels in real-time.
	Participants are commenced on once daily dose of 150 IU	Participants will be commenced on oral	

		
Capsulin, at the end of the meal challenge. They are provided with lunch half an hour after the oral insulin dosing, and observed for a further 2h prior to discharge.
 
Participants are educated on the appropriate timing of the oral insulin dosing: Capsulin is to be taken half an hour before a main meal.
 
Review home hypoglycaemia management with participant &/or parent. Provide oral insulin for a week
	
insulin 150 IU OD, to ensure stability of the closed loop algorithm. Dose increased to 150 IU BD after one week
 
As per ISPAD & Diabetes Australia guidelines.

VISIT 2 (Week 1)	1.5h	Clinical review of total insulin dose, insulin sensitivity factors, insulin-carbohydrate ratios and CGM metrics.	
		Assessment of Capsulin use, and adverse events	Review of logbook and Aardex history
		Commenced on twice daily 150 IU Capsulin– with appropriate education of use. Provide oral insulin for 5 weeks	
VISIT 3 (Week 6)	45 min	Pump download for pump settings and CGM data. Clinical review of total insulin dose, insulin sensitivity factors, insulin-carbohydrate ratios and CGM metrics.	
		Assessment of Capsulin use, and adverse events	Review of logbook and Aardex history
		Provided with further Capsulin for remaining 6w; twice daily 150 IU dose. Participants are educated on the appropriate timing of the oral insulin dosing: Capsulin is to be taken half an hour before two main meals.	
		Participant to return Dexcom G6 transmitter to researcher	
VISIT 4 (week 12) (STUDY END)	6.5h	Height, weight, BP,	
		
Pump download for pump settings and CGM data
 
Glycaemic measures: HbA1c, total insulin dose, insulin sensitivity factors,
	

		insulin-carbohydrate ratios and CGM metrics	
		Metabolic measures (2mls blood): lipid profile, liver function tests	Fasting bloods
		Meal Challenge (following an overnight fast) with an oral insulin pre-meal bolus. Measure gut hormone responses over 5h - plasma GLP-1 (glucagon like peptide), GIP (glucose dependent insulinotropic polypeptide), plasma glucagon and free insulin. A total of 106 mls will be drawn for 15minutely blood BGL testing and gut hormones during the meal challenge.	
		Participant report of outcomes determined – Appetite and impact on dietary intake, perceived weight loss and well-being.	
VISIT 5 (14w)	30 min	Pump download for pump settings and CGM data	This visit is to ensure that participants are back on baseline therapy.

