## 2.2 Intervention

*Name and description of the intervention or product(s) used in this trial, including investigational product(s) and comparator product/s (if applicable). Include status of product registration (i.e. registration on Australian Therapeutic Goods Registry, or equivalent).*

1. Oral insulin: Capsulin (Diabetology Ltd) 150 IU once a day, increased to twice a day after a week; to be administered half an hour before food for study duration. This investigational product has been trialled in type 2 diabetes, but not in type 1 diabetes.
2. Hybrid closed loop (HCL) insulin delivery system – Medtronic 670G or Medtronic 770G. This will be the participant's own insulin delivery system
3. Dexcom G6 for participants on Medtronic 670G, as the Medtronic 670G does not have the follow-function to enable monitoring of these participants whilst on the investigational oral insulin.
4. Track caps (Aardex) – The oral insulin capsules will be provided to the participants in bottles fitted with caps which will track how many times the bottles are opened and at what time of day they will be opened. We have used this system effectively in a previous clinical trial (AdDIT-RGS0000002353)

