**NOTE:**

Visits 1 and 4 are face-to-face; however other visits can be done via telehealth if required.

\*In the 1st three weeks from commencement of the oral insulin, participants will be followed in real-time using the follow-function of the closed loop system or Dexcom G6. Low alerts will be enabled on the phone which will permit immediate correction of hypoglycaemia. Adjustments will be made to the pump settings if required.

\*Subsequently, there will be weekly contact with the participants by research staff to monitor and review CGM and pump data to make adjustments to pump settings (if required) and to monitor safety.

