## 8.2 Safety

1. The safety parameters and the methods and timing for assessing, recording, and analysing safety parameters. Include a description of emergency procedures if applicable. Risk of hypoglycaemia/hyperglycaemia:

The risk of hypoglycaemia with oral insulin is negligible. However, any patient receiving insulin at any time has the potential to develop hyper or hypoglycaemia.

- a. The sensor glucose levels of all study participants are available to participants in real-time which will enable them to take appropriate clinical action as required. Participants will also be followed in real-time by research staff in the first three weeks of the study with commencement of oral insulin.
- b. Hybrid closed loop system is semi-automated and is dependent on the sensor glucose levels and basal insulin delivery will be adjusted based on sensor glucose readings. HCL is therefore expected to mitigate any risk of hypo/hyperglycaemia while on oral insulin

2. Risk of immediate allergic reactions with oral insulin

All participants will be monitored after the first dose for at least 30 minutes.

Emergency procedures:

- For severe hypoglycaemia, intramuscular glucagon can be administered.
- For ketosis > 0.6mmol/l with glucose > 15mmol/l, insulin (rapid-acting) is administered with an insulin pen.

This is taught to every family at the time of diagnosis of T1D and review of their knowledge is established in subsequent clinic follow-ups.

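### Visit 1 issues Dexcom G6 sensors for two weeks, but 670G users are to be followed in real time for three, and no resupply is listed

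*Protocol*

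**What the plan says.** Section 2.2 explains why 670G users are given a Dexcom G6: "as the Medtronic 670G does not have the follow-function to enable monitoring of these participants whilst on the investigational oral insulin". The 770G has a follow-function and needs no second sensor.

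In section 4.8, the Visit 1 (week 0) row covers Dexcom set-up and training for 670G users and states the supply: "Provided with sufficient sensors for 2 weeks". The comment cell beside it gives the purpose of the device as "to obtain glucose data during the first three weeks of the study period".

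The note under the schedule applies to the first three weeks of oral insulin and says that "participants will be followed in real-time using the follow-function of the closed loop system or Dexcom G6". It ties low-glucose alerts and pump adjustments to this period, and moves to weekly contact afterwards. Section 8.2 repeats the measure as a safety provision: "Participants will also be followed in real-time by research staff in the first three weeks of the study with commencement of oral insulin".

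The later rows say nothing about more sensors. Visit 2 (week 1) lists a capsule supply. Visit 3 (week 6) lists a capsule supply and the return of the Dexcom transmitter.

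**The concern.** Two cells of one table row describe the same device, the same users and the same start date, and they give different durations. The supply line states how long the sensors are meant to last, and that is a week less than the period for which the device is issued.

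The monitoring itself is a safety measure. Oral insulin is being added to a closed-loop system, starting once daily and stepping up to twice daily after one week. For 670G users the Dexcom is the only route the protocol gives by which staff can see glucose in real time. If a site works from the supply line alone, staff viewing of these participants lapses at day 14, one week after the step up. 770G users would be followed for the full three weeks, so the two pump groups would get different safety oversight without anyone having intended it.

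**Working it through.** No power, alpha or event figure is involved. The check compares two stated durations and looks through the visit rows for anything that closes the gap.

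**Inputs**

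| Item | Value | Source (Protocol) |
|---|---|---|
| Sensors issued at Visit 1 | 2 weeks = 14 days | 4.8, Visit 1 |
| Period the Dexcom is to cover | 3 weeks = 21 days | 4.8, Visit 1 comment |
| Real-time following | 3 weeks from first dose | 4.8 note; 8.2 |
| First oral insulin dose | Visit 1, after the meal challenge | 4.8, Visit 1 |
| Step to 150 IU twice daily | after week 1 | 4.8, Visits 1 and 2 |
| Sensors listed at Visits 2 and 3 | none | 4.8 |

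Dexcom set-up and the first dose fall on the same visit, so both periods run from the same day and can be subtracted directly.

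**Sensor coverage**

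- Shortfall = required − supplied = 21 − 14 = 7 days, or 1 week.
- Coverage = 14 / 21 = 67%.
- The uncovered days are 15 to 21.

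**Coverage on the full dose**

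- Followed days on twice-daily dosing = 21 − 7 = 14 (days 8 to 21).
- Of these, covered by the written supply = 14 − 7 = 7 days, so 7 / 14 = 50%.

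**Does another row close the gap?**

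- Visit 2, at week 1, would be in time, but lists only capsules.
- Visit 3, at week 6, would be too late for week 3, and lists only capsules and the transmitter return.

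**Comparison with the capsule supply in the same table**

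- Visit 1: "Provide oral insulin for a week"; Visit 2: "Provide oral insulin for 5 weeks"; Visit 3: "Provided with further Capsulin for remaining 6w".
- Total = 1 + 5 + 6 = 12 weeks, against 12 weeks of dosing; shortfall = 12 − 12 = 0.

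The capsule lines add up to their stated period. The sensor line does not.

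**After correction**

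- Three weeks at Visit 1, or 2 + 1 weeks over Visits 1 and 2, gives 21 / 21 days and no shortfall.

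**The case against.** The strongest reply is that this is an unlisted supply step and not a contradiction. The sensor line says what is handed over at Visit 1; it does not say that Dexcom use ends there. The duty to follow for three weeks is stated three times and never varied, so stopping at day 14 would itself breach the protocol. A later issue also fits the schedule: Visit 2 falls a week before the first supply runs out, and the transmitter stays with the participant until week 6. If Visit 2 is by telehealth, as the note allows, five weeks of capsules must still reach the participant, and sensors can travel the same way. The capsule comparison is imperfect too, because the investigational product is subject to accountability counts and sensors are not.

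Most of this stands. The intended period is three weeks, resupply is feasible, and a site that reads the whole protocol would probably arrange it. The capsule comparison is supporting evidence only. What remains is that the schedule staff work from gives a supply one week short of the period in the adjoining cell, and no text says when or how the third week is provided.

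It is also fair to say that the consequence is limited. Under section 8.2 participants see their own sensor glucose in real time and the closed loop adjusts basal insulin. Sections 7.2 and 8.4 keep weekly review of sensor and pump data going throughout.

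**Conclusion.** The inconsistency is real and minor. As written, the sensor supply for each 670G user falls 7 days short of the 21 days of real-time following, in one of the two followed weeks on twice-daily dosing. The gap is zero if sensors are reissued by day 14, which the protocol neither requires nor rules out.

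The result assumes that sensors start at Visit 1 and that the listed supplies are the only ones. Wear time per sensor is not given and is not needed, since the supply is stated in weeks. The number of 670G users is not given either; among 10 completers it can lie anywhere from 0 to 10, so the total shortfall lies between 0 and 10 sensor-weeks.

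The sample size, the primary outcome (change in subcutaneous insulin dose) and the planned analysis are unaffected. The point should be fixed because it concerns the delivery of a stated safety measure and is easily put right.

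**What to change.** In section 4.8, do one of the following:

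- change the sensor supply in the Visit 1 row from two weeks to three; or
- keep two weeks at Visit 1 and add a one-week sensor resupply for 670G users to the Visit 2 row, to be posted in time to arrive by day 14 if that visit is by telehealth.

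The first is simpler and does not depend on how Visit 2 is held. The three-week period in the comment, the note and section 8.2 needs no change.

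The cost is one table line and at most one additional sensor-week per 670G user: no more than 10 sensor-weeks for 10 completers, plus one for any replaced 670G participant who reaches the third week.

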**NOTE:**

Visits 1 and 4 are face-to-face; however other visits can be done via telehealth if required.

\*In the 1st three weeks from commencement of the oral insulin, participants will be followed in real-time using the follow-function of the closed loop system or Dexcom G6. Low alerts will be enabled on the phone which will permit immediate correction of hypoglycaemia. Adjustments will be made to the pump settings if required.

\*Subsequently, there will be weekly contact with the participants by research staff to monitor and review CGM and pump data to make adjustments to pump settings (if required) and to monitor safety.

**4.9 Trial Termination**

Study participation is voluntary, and participants may withdraw at any time.

In general, once a participant is in the study, he/she will remain in the study unless the investigator believes it is not safe for the participant to continue. The criteria below will be used to determine safety:

1. Severe hypoglycaemia (seizure or coma or any episodes requiring glucagon).
2. Severe diabetic ketoacidosis (venous ph <7.2)

3. Non-compliance with the medication which in the judgment of the investigator increases risk for the participant

#### Criteria for Suspending/Stopping Overall Study

The DSMB will provide guidance to the Lead Investigator as to whether the overall study should be stopped. This will be conveyed to the ethics committee within 72h of the DSMB notification.

#### 4.10 Data identification

Every participant will be given a unique study number. All data on the CRFs will be de-identified

### 5 Source and Selection of Participants

#### 5.1 Source of Participants

We will recruit 10 individuals with type 1 diabetes attending the diabetes service of Perth Children's Hospital, Fiona Stanley Hospital and Sir Charles Gardiner. We will also recruit using social media (Facebook, Twitter), DRWA and NDSS. Recruitment will be over 6 months.

#### 5.2 Participant inclusion criteria.

1. T1D of at least 1 year duration,
2. C-peptide < 0.1nmol/l (in the absence of hypoglycaemia)
3. Age 16 - 25 years
4. On Medtronic 670G/770G (using closed loop system for  $\geq 70\%$  of the time in last 2 weeks)
  - No plans to change the management during the study period.
5. HbA1c < 7.5%
6. Ready to meet the requirements of the protocol.
7. Has the ability to download the insulin pump if on Medtronic 670G (Medtronic 770G users have automatic download)
8. English speaking, living in an area with internet and cellular phone coverage

#### 5.3 Participant exclusion criteria.

1. Recent significant change in HbA1c exceeding 1.5% over the past 3 to 4 months.
2. Use of any non-insulin glucose-lowering agent.
3. Pregnancy, comorbidities: Renal dialysis/transplant or glomerular filtration rate <60ml/min/m^2, malabsorption, coeliac disease, active liver disease, islet cell/pancreatic transplant

#### 5.4 Participant withdrawal criteria

Participants can withdraw at any time from the study, without having to provide a reason for doing so. Those who withdraw from the study after commencing on oral insulin, will be asked to return all unused capsules to the research unit. They will not require any follow-up as the insulin is a quick acting insulin, without any carry-over effects.

Participants who withdraw from the study will need to be replaced, as the study is powered for a sample size of 10 with completed data.

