improvement in the lipid profile with 10% improvement in LDL and total cholesterol and 20% for triglycerides. These promising findings open up avenues to explore the potential of oral insulin in people with T1D.

*Proposed Study:* This pilot study will expand on the findings from these previous studies by exploring the utility of oral insulin in individuals with T1D over a 12-week period.

The proposed study aims to provide preliminary data of whether oral insulin is acceptable and can be used as an adjunct therapeutic intervention in individuals with T1D, and to use the information obtained to inform a future randomised controlled trial specifically designed to assess the efficacy of oral insulin as an adjunct to current insulin therapy. The 12-week study will provide sufficient duration to review glycaemic outcomes that can be measured by HbA1c and metrics from continuous glucose monitoring (CGM) which include time in hypoglycaemia, time in target glucose range and time in hyperglycaemia. We predict a reduction in total subcutaneous insulin dose with supplemental oral insulin will lead to a reduction of systemic hyperinsulinemia. This in turn, has the potential to further reduce hypoglycaemia, which still remains a concern in individuals with T1D (9, 10). This study will also enable us to explore trends of glycaemic variability with daily oral insulin therapy. Improvement in these glycaemic measures are known to reduce the long-term risk of diabetes macro and microvascular complications (11, 12). Liver is the primary site of insulin delivery with oral insulin, unlike subcutaneous insulin, where systemic insulin levels are high in target organs which include liver, muscle and adipose tissue. Hence, the study will also review metabolic parameters with the potential role of oral insulin being cardio-protective.

Our ultimate aim is to improve our understanding of oral insulin and make recommendations for future research to enhance improvements in clinical care to better support people with T1D.

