### 4.6 Intervention/Product Description

Capsulin™ is, an oral insulin developed by Diabetology Ltd and is based on their patented Access delivery system (5). Capsulin is an enteric-coated capsule which contains unmodified human recombinant insulin with a mixture of well-characterized and “generally regarded as safe” (GRAS) substances which facilitate the transport of insulin through the intestinal wall and into the portal circulation. The capsule is stable at room temperature for 18 months.

Capsulin comes in 150 IU dose capsules, and will be provided to the participants in bottles fitted with a tracking cap (Aardex), which have been effectively used in a previous clinical trial – AddIT (RGS0000002353), to monitor adherence to prescribed dose and time of dosing.

Dose: Capsulin 150 IU BD

This dose is chosen as higher dose (300 IU BD) has no added benefit in a Phase 2A study (8). Oral insulin is absorbed over a period of 1-2 hours and slowly increases to a peak at about 4-5 hours post ingestion. Data suggest that 150 IU dose leads to a reduction of 2 mmol/mol in blood glucose. Capsulin delivers insulin to the liver, where it suppresses hepatic glucose production. As the production of glucose within the liver is related to the concentration of the glucose in the bloodstream, increasing the dose of Capsulin between 150 IU and 300 IU does not lead to a greater fall in glucose. Dose of 150 IU BD resulted in reduction in HbA1c and improvement in metabolic profile with no side-effects.

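### Section 5.4 waives follow-up after early stopping on drug carry-over alone, so an event-free early stopper lacks the return-to-baseline check that completers get at Visit 5

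*Protocol*

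**What the plan says.** Section 5.4 lets participants leave at any time without giving a reason. Those who leave after starting Capsulin are asked to hand back unused capsules, and then: "They will not require any follow-up as the insulin is a quick acting insulin, without any carry-over effects". No other ground is given.

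The notes under the visit table in section 4.8 let staff alter pump settings while participants take the drug. This may happen during the first three weeks of real-time following, and afterwards through "weekly contact with the participants by research staff to monitor and review CGM and pump data to make adjustments to pump settings (if required").

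The last row of the same table is Visit 5 at week 14, a 30-minute contact with a pump and CGM download. Its stated purpose is: "This visit is to ensure that participants are back on baseline therapy". The notes require only Visits 1 and 4 to be face-to-face and add that "other visits can be done via telehealth if required". The table is introduced with "The visits, assessments and visit duration for every participant is listed in the table below".

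Section 4.9 adds a second route out, removal by the investigator. Its criteria are severe hypoglycaemia, severe ketoacidosis, and non-compliance judged to raise the participant's risk. Section 8.5 leaves follow-up after an adverse event to the study doctor. Section 9.5 names a single analysis set, participants with complete 12-week data.

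**The concern.** The reason in 5.4 answers whether any insulin effect remains after the last capsule. It does not answer whether the pump is still programmed for a participant who takes Capsulin. Absence of drug carry-over is equally true of someone who stops at week 12, and the protocol still schedules a check for that person. It therefore already accepts that stopping Capsulin calls for a check unrelated to residual drug, and 5.4 drops that check for early stoppers without addressing its purpose.

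What is at stake is participant safety on a small scale. Entry requires C-peptide below 0.1 nmol/l (section 5.2), so participants have little insulin of their own to cover a pump left at altered settings. There is also a reporting consequence. Safety and retention are outcomes in section 7.1, but the only analysis set in 9.5 leaves out anyone who stopped early.

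**Working it through.** The protocol gives no figure to reproduce on this point. The check sets its provisions side by side.

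**1. When can settings be changed on drug?** Real-time following covers weeks 1 to 3, and weekly contacts cover the rest: 12 − 3 = 9 weeks, or about nine contacts. An early stopper at any time may therefore have had settings changed, though only where staff judged it necessary.

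**2. Who gets a scheduled check after the last dose?**

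| Participant | Off-drug provision | Source | Scheduled checks |
|---|---|---|---|
| Completer | Visit 5, (14 − 12) × 7 = 14 days after week 12 | 4.8 | 1 |
| Stops with an adverse event | Follow-up as the study doctor decides | 8.5 | discretionary |
| Withdraws without an adverse event | None; return capsules only | 5.4 | 0 |
| Removed for non-compliance without an adverse event | None stated | 4.9 | 0 |

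The first two removal criteria in 4.9 are also severe adverse events under 8.4, so 8.5 covers them. Non-compliance need not involve an event. The gap is therefore wider than voluntary withdrawal.

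**3. Does the visit table already cover early stoppers?** Its introduction refers to every participant. If that is meant to bring early stoppers to Visit 5, then 5.4 contradicts it. If not, early stoppers have no check. The sentence in 5.4 needs changing on either reading.

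**4. Does the closed loop make the check unnecessary?** Sections 8.1 and 8.2 credit the loop with adjusting basal delivery, and 8.2 calls it semi-automated. Section 8.4 speaks more loosely of insulin settings being adjusted. The clinical reviews in 4.8 also cover carbohydrate ratios and sensitivity factors, and nothing in the protocol says the loop corrects these once changed. Completers use the same loop and are still given Visit 5.

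**5. What would the existing check cost?** Scheduled visit time for a completer is 8.5 + 1.5 + 0.75 + 6.5 + 0.5 = 17.75 h. Visit 5 is 0.5 / 17.75 = 2.8% of that. No dropout rate is given. For an assumed 1 to 3 early stoppers, Visit 5 adds 0.5 to 1.5 h in all.

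**The case against.** The strongest reply is that harm needs several things to go wrong together. A setting must have been changed, the participant must stop without an event, the setting must stay unrestored, and the loop must fail to compensate. The protocol gives no frequency for any of these. The pump is the participant's own, entry requires closed-loop use for at least 70% of the preceding two weeks, and glucose is visible in real time. Families are taught how to respond to ketosis, and Visit 1 stores the baseline settings. Saying that follow-up is not required does not forbid it. Completers, too, may spend about 14 days off drug before Visit 5, since Visit 4 lists a download but no reset step. All of this stands. It keeps the risk modest, but it does not supply the missing check.

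Three stronger readings are tempting and are not supported.

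- A reader might infer that settings will usually have been weakened, because section 2.1 says "We predict a reduction in total subcutaneous insulin dose with supplemental oral insulin". The loop can lower the delivered dose with no programmed setting changed, so a lower dose does not show weaker settings.
- A reader might size the glucose rise from section 4.6: "Data suggest that 150 IU dose leads to a reduction of 2 mmol/mol in blood glucose". That would mean reading the printed unit as mmol/l, assuming settings were weakened by exactly the drug's effect, and ignoring the loop. The result would not be a risk estimate.
- A reader might take the remark in 8.2 about the loop's protection during oral insulin use to mean that protection ends with the drug. That section is about risks of the drug and does not say so.

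**Conclusion.** The point holds as an inadequately grounded rule. Section 5.4 waives follow-up for a reason that does not reach pump settings, while the protocol gives completers of the same drug a check for that purpose. The size is a count: one scheduled off-drug check for a completer, none for a participant who withdraws or is removed for non-compliance without an adverse event. No glucose magnitude should be attached to it.

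The conclusion assumes that the protocol is followed as written and that no separate handover procedure exists. It does not assume that settings were changed in any given participant. The 12-week paired estimates are not affected. This is a cheap improvement to participant safety and to the completeness of safety and retention reporting.

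**What to change.** Replace the no-follow-up sentence in 5.4 with:

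> Anyone who stops Capsulin early will be offered, and may decline, a review of pump settings against the Visit 1 download at stopping, and the Visit 5 pump and CGM download (30 min, telehealth allowed) about two weeks after the last dose.

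This wording covers removal under 4.9 as well as withdrawal. Follow-up of adverse events stays under 8.5.

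Add to 9.5:

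> Safety and retention are summarised for all who took at least one dose; the 12-week paired analysis keeps its current set.

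An optional addition serves aim 2, acceptability. Section 7.2 gives the self-report questionnaire only at study end, so early stoppers have none planned. It could be offered at stopping and listed separately, since the responses will be too few for more than a listing.

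The cost is two text edits, one short review at stopping (the protocol gives no duration from which to price it) and one 30-minute contact per early stopper. Some will decline, so the gap narrows but may not close.
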